7.6.2 Adverse Events of Interest

The following adverse events of special interest will be listed and summarized by treatment groups during the DB period.

- Pre-specified liver function abnormalities
- Infections: All reported infections and infestations within the System Organ Class (SOC): *Infections and infestations*. The severity of serious infections will be summarized.
- Malignancy: All reported events defined in MedDRA Maintenance and Support Services Organization (MSSO) Structured MedDRA Query (SMQ) list.
- ~~Blood pressure related AE~~
- Hypertension: All reported events defined in pre-specified MedDRA code of hypertension.

- Neutropenia: All reported events defined in pre-specified MedDRA code of neutropenia.
- Thrombocytopenia: All reported events defined in pre-specified MedDRA code of thrombocytopenia.
- Demyelinating disorders: All reported events defined in MedDRA Maintenance and Support Services Organization (MSSO) Structured MedDRA Query (SMQ) list.
- Autoimmune diseases: All reported events defined in pre-specified MedDRA code of autoimmune disorders.

7.6.3 Deaths

All AEs with the outcome of death reported during the study will be listed together with a clinical narrative relating to the death of the subject. All reported deaths after a subject is enrolled will be listed separately by subject.

7.6.4 Other Serious Adverse Events

SAEs are captured on an eCRF page. All SAEs and related SAEs will be summarized by treatment group and listed together with a clinical narrative.

7.6.5 Adverse Events Leading to Discontinuation of Study Therapy

AEs leading to discontinuation of study drug are identified on the eCRF will be summarized and listed together with a clinical narrative.

7.6.6 Multiple Occurrences of Adverse Events

Several descriptive summaries of adverse events that takes into account the number of occurrences that an AE was reported by individual subjects will be provided. In order to prepare these summaries, the CRF data will be processed according to standard BMS algorithms to categorize each line of subject data as a new occurrence or a continuation of an existing event. This determination will be based upon onset and resolution dates. Each line of subject data will represent the maximum severity observed as well as the last known assessed relationship to study medication by the investigator.

The number and proportion of subjects who experienced an AE once or multiple times (0 Events, 1 Events, 2-3 Events, ≥ 4 Events) will be summarized by treatment groups for most common AE (at least 5% subject in any treatment group) and event of special interest, infections.

Listing displaying the unique instances of all AEs will be provided.

Note: The unique instances of all AEs will be generated after duplicates have been eliminated and overlapping and contiguous occurrences of the same event have been collapsed.

7.6.7 Summaries of Laboratory Data

The results of all protocol-specified clinical laboratory tests, as well as laboratory results outside of the normal range, will be listed. Scheduled laboratory measurements and corresponding change from baseline values will be summarized by treatment and nominal visit for each laboratory test for the MITT analysis population.

The frequency of subjects with any marked laboratory abnormality will be presented by laboratory test for the DB period. The results are based on the As-treated analysis population. The criteria used for classifying laboratory test results as markedly abnormal will be listed.

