- Introduce new dose(s) arms if needed and enroll up to about 82 subjects per new arm
- Complete full enrolment for all efficacious arms (up to about 82 subjects per arm)
- Stop the study enrollment if all dose arms are stopped for safety or futility.

The total sample size (range from 328 to 408 subjects) varies depending on actual enrollment rate, number of dropped dose arm(s) and number of newly added dose arm(s). The details of interim analysis and the criteria to adapt dose arm(s) and stop for futility are specified in the [section 8.5](#).

Endpoints:

Co-Primary

- ACR20 response rate at Week 12
- ACR70 response rate at Week 12

Secondary

- Signs and Symptoms: ACR20/ACR50/70 over time
- Remission and change from baseline: DAS28-CRP, DAS-ESR, SDAI, CDAI, Boolean over time
- PK: Ctrough of BMS-986142
- Change in RAMRIS Scores of synovitis, osteitis, bone erosion and cartilage loss from baseline to Week 4 and Week 12

Statistical Analyses:

Efficacy analysis:

The co-primary endpoint ACR 20 and ACR70 response rate at Week 12 will be summarized for each treatment group using point estimate and 90% confidence intervals (CIs). Treatment difference of ACR 20/ACR70 response rate at Week 12 between each BMS-986142 arm versus placebo will be provided with point estimate and two-sided 95% CIs. The chi-square tests will be used to compare the ACR response rates at Week 12 between each of the active treatment arms and the placebo arm at type I error rate of 0.05. Within each treatment group, the statistical testing will be performed for ACR20 at level of 0.05 first. If it is statistically significant, then the statistical testing will be performed for ACR70. Otherwise, stop testing for this treatment group. All treatment groups will follow the

same testing procedure. All subjects who discontinue prematurely during the treatment period or receive rescue therapy will be counted as non-responder at subsequent visits.

Safety analysis:

All safety presentations will be based on the As-Treated population. Frequency distribution and individual listings of all adverse events, laboratory abnormalities and vital signs will be generated. Changes in clinical laboratory test results from baseline will be provided. No formal statistical tests on the treatment difference will be performed for any safety analyses.

Pharmacokinetic analysis:

Ctrough values will be descriptively summarized by treatment and study days.

[figure not shown]
[figure not shown]
[figure not shown]

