8.4.3 Safety Analyses

All recorded adverse events will be listed and tabulated by system organ class, preferred term and treatment. Vital signs and clinical laboratory test results will be listed and summarized by treatment. Any significant physical examination findings, and clinical laboratory results will be listed. ECG readings will be evaluated by the investigator and abnormalities, if present, will be listed. The pre-established Events of Special Interest will be listed and summarized. The safety summaries will be performed using all treated subjects.

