6.3 Populations for Analyses

- All Enrolled Subjects: All subjects who sign an informed consent.
- All Randomized Subjects: All subjects who are randomized to a treatment.
- Modified Intent-to-Treat (MITT) Analysis Population: All randomized subject who have received at least one dose of the study medication. Subjects will be grouped according to the treatment to which they were randomized by IVRS at the start of the study. The MITT analysis population will also be referred to as “All Randomized and Treated Subjects”.
- As-Treated Analysis Population: All Subjects who have received at least one dose of study medication. Subjects will be grouped according to the treatment that they actually received as opposed to the treatment to which they were randomized. Subjects will be grouped on an as randomized basis unless the subject received the incorrect medication for the entire period of treatment. In that case, the subject will be analyzed in the treatment group associated with the incorrect medication he/she received.
- Efficacy Analysis Population: This is a subset of the MITT Analysis Population where the subjects who are randomized to a treatment arm and discontinued based on the interim analysis are excluded. All efficacy results involve statistical comparison or modeling will be based on this analysis population unless otherwise specified.
- [REDACTED]
- [REDACTED]
- Pharmacokinetic Population: All subjects who have received BMS-986142 and have any available concentration-time data.

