7.6 Safety

Analysis of all safety data will follow the BMS standard safety data conventions^{[11](#) [12](#)} and supplements to the standard conventions as defined in this document.

The evaluation of drug safety is based primarily on clinical AE, laboratory abnormalities and vital signs reported during the study.

The summaries of AEs and laboratory marked abnormality during DB period will be provided by treatment groups. AEs and laboratory marked abnormalities will be included in the analysis of the DB period if the onset date is on or after first dose date and event occurs within 30 days post last dose date (DB period).

Frequency distribution and individual listings of all AEs will be generated. Laboratory marked abnormality using pre-defined abnormality criteria will also be descriptively summarized. There will be no statistical testing of group difference with respect to frequencies of AEs or laboratory marked abnormalities.

All recorded adverse events will be listed and tabulated by system organ class, preferred term, treatment and overall. Any physical examination findings will be listed. ECG, vital signs and clinical laboratory test results and corresponding change from baseline values will be listed and summarized by treatment. Values for ECG, vital signs and clinical laboratory test results outside the pre-specified criteria will also be listed and summarized. ECG readings will be evaluated by the Investigator and abnormalities, if present, will be listed.

Unless otherwise specified, baseline is defined as the last non-missing result with a collection date-time less than the date-time of the first dose of study medication, for laboratory results, vital signs and ECG.

Presentations for the DB period will be provided by “as treated” treatment group for as-treated analysis population, unless otherwise specified.

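### SAP 7.6.7 puts laboratory values and changes from baseline on the MITT population, contrary to the protocol synopsis, which bases all safety presentations on As-Treated; only wholly misallocated or unrandomised subjects are affected

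*SAP*

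**What the plan says.** The protocol synopsis, under its safety analysis paragraph, states: "All safety presentations will be based on the As-Treated population". The same paragraph goes on: "Changes in clinical laboratory test results from baseline will be provided". Laboratory changes are therefore within the scope of that rule. Protocol 8.4.3 adds: "The safety summaries will be performed using all treated subjects".

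SAP 7.6 sets a matching default. Presentations for the double-blind period go by the as-treated "treatment group for as-treated analysis population, unless otherwise specified".

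SAP 7.6.7 then treats two kinds of laboratory table differently:

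- Scheduled values and changes from baseline are "summarized by treatment and nominal visit for each laboratory test for the MITT analysis population".
- For marked abnormalities, "The results are based on the As-treated analysis population".

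SAP 6.3 defines how each population is grouped. For MITT: "Subjects will be grouped according to the treatment to which they were randomized by IVRS at the start of the study". For As-Treated: "Subjects will be grouped on an as randomized basis unless the subject received the incorrect medication for the entire period of treatment". In that one case the subject moves to the group of the medication received.

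**The concern.** Two tables built from the same blood samples, in the same SAP section, use different populations, and one of them departs from the protocol. Within SAP 7.6 the laboratory value and change table is the only summary assigned to MITT. The ECG and vital-sign summaries name no population and so take the As-treated default. No reason is given for the exception, and it reads like a drafting slip.

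It deserves correcting because laboratory change by dose is a safety readout in a dose-ranging trial. Protocol 1.5 says that the only safety signal identified so far is a possible mild, reversible rise in transaminases. If a subject took the wrong treatment throughout, the transaminase change would be averaged into a dose that the subject never took, while a marked abnormality in the same subject would be counted under the dose taken. A reader comparing the two tables could not reconcile them from the report alone.

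**Working it through.** The plan gives no figure to reproduce. The check is a comparison of rules, followed by simple arithmetic on the size of one misplaced subject.

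**Step 1: which grouping applies to the laboratory change table.** SAP 7.6.7 says only that the table is by treatment. Grouping by randomised arm is an inference from SAP 6.3, which builds the randomised grouping into the definition of MITT.

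**Step 2: where the two populations place each kind of subject.**

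| Subject | Laboratory values and changes (MITT) | Marked abnormalities and AEs (As-Treated) |
|---|---|---|
| Randomised, took the assigned drug | Randomised arm | Randomised arm |
| Randomised, wrong drug for part of treatment | Randomised arm | Randomised arm |
| Randomised, wrong drug for all of treatment | Randomised arm | Arm received |
| Treated without randomisation | Not included | Included |

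Only the last two rows differ.

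**Step 3: how the third row could arise.** Protocol 4.4 has IVRS assign container numbers at each dispensing visit, and protocol Table 5.1-2 marks dispensing at Day 1, Week 4 and Week 8. A subject who completes treatment would need the wrong medication from all three dispensings. A subject who stops before Week 4 would need only one such error. The documents give no frequency for either.

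**Step 4: the size of one such subject.** Take a planned arm of n = 82 (protocol 8.1).

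- Share of the arm: 1/82 = 1.2%.
- Denominators: if one subject is moved, MITT has 82 in both arms, while As-Treated has 82 − 1 = 81 in the randomised arm and 82 + 1 = 83 in the arm received.
- Let d be the subject's change from baseline and m the mean change of the other subjects in the arm. Including the subject shifts the randomised arm's mean by (d − m)/82.
- For illustration only, assume d = 200 U/L for ALT and m = 0. The shift is 200/82 = 2.4 U/L. The documents do not supply the 200; the shift is proportional to it, so half the rise gives half the shift.

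The protocol synopsis announces that recruitment stops before the planned number, so arms may be smaller. With the same assumed rise, an arm of 40 (the size protocol 8.5 gives for an added suboptimal-dose arm) has 1/40 = 2.5% and 200/40 = 5.0 U/L. An arm of 20 (the size at the interim analysis) has 1/20 = 5% and 200/20 = 10 U/L.

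**The case against.** The best defence is the exception clause in SAP 7.6. The as-treated default holds unless a section specifies otherwise, and SAP 7.6.7 does. This stands as far as it goes: the SAP does not contradict itself, and the table can be programmed as written. It does not reconcile the SAP with the synopsis, whose rule covers all safety presentations without qualification, and it does not explain why the next paragraph of SAP 7.6.7 goes the other way.

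Three stronger readings are tempting, and the documents do not support them.

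- *Any misdosed subject would appear under the wrong dose.* This is too broad. Under SAP 6.3 a subject misdosed for part of treatment stays in the randomised arm in both populations, and changing the population would not move that subject.
- *Protocol 8.4.3 is a second, independent conflict.* It is not a clear one. It asks for all treated subjects, which protocol 8.2 defines by receipt of at least one dose, with no grouping rule. Drug is dispensed after randomisation, so by design the treated subjects and the MITT subjects are the same people. The protocol conflict rests on the synopsis.
- *The liver signal would be obscured, or the tables would disagree on dose relationship.* Neither is shown. Marked laboratory abnormalities are As-Treated. Pre-specified liver function abnormalities are an event of interest (SAP 7.6.2) and laboratory AEs are in the AE tables (SAP 7.6.1), both under the As-treated default. All laboratory results are listed. One subject changing arms could make the tables differ, but need not change any dose pattern.

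It is also fair to say that the table is descriptive. No safety testing is planned, and the interim safety endpoints specified in protocol 8.5 and SAP 7.9 are adverse events and vital signs, not laboratory means.

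**Conclusion.** The inconsistency is real: for laboratory values and changes from baseline, SAP 7.6.7 names a population that the protocol synopsis rules out. It also differs, without a stated reason, from the population used for marked abnormalities in the same section.

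The consequence is small and contingent. It needs at least one subject who took incorrect medication for the whole treatment period, or who was treated without being randomised. If there is none, the tables are identical under either population. The conclusion assumes that the randomised grouping in SAP 6.3 carries over to SAP 7.6.7; a programmer who kept the as-treated grouping within MITT would lose only unrandomised subjects. This is a minor alignment point that affects no efficacy result, error rate or stated decision rule.

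**What to change.** In SAP 7.6.7, name the As-treated analysis population in place of MITT for the summaries of laboratory values and changes from baseline. Both laboratory tables then use one population and one set of denominators, in line with the synopsis and the SAP 7.6 default.

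The cost is one phrase. No new data are needed and no efficacy analysis changes. It can go into the same SAP update that brings the sample-size section into line with the protocol, since SAP 5 still describes a mainly TNF-IR population and protocol 8.1 a mainly MTX-IR one. The change should be made before unblinding.

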7.6.8 Other Safety Considerations

7.6.8.1 ECG

Summary statistics (n, mean, standard deviation, median, minimum, and maximum) will be presented for each ECG parameters and the corresponding changes from baseline by treatment and visit. The baseline value is defined as the last measurement before the first dose. ECG readings will be evaluated by the Investigator and abnormalities, if present, will be listed.

The frequency distribution of subjects' maximum recorded post-dose QTcF, PR, QRS and Δ QTcF will be tabulated by treatment and summarized within the CSR text for the following ranges:

For QTcF: $QTcF \leq 450$ msec, 450 msec $<$ $QTcF \leq 480$ msec, 480 msec $<$ $QTcF \leq 500$ msec, $QTcF > 500$ msec

For PR: $PR \leq 200$ msec, $PR > 200$ msec

For QRS: $QRS \leq 120$ msec, $QRS > 120$ msec

For Δ QTcF: $\Delta QTcF \leq 30$ msec, 30 msec $<$ $\Delta QTcF \leq 60$ msec, $\Delta QTcF > 60$ msec

Individual QTcF, PR, QRS or Δ QTcF values meeting these criteria will be flagged in the data listing.

7.6.8.2 Vital Sign

Vital signs parameters (systolic blood pressure, diastolic blood pressure, heart rate, respiratory rate and body temperature) will be listed. Summaries of vital sign parameters will be provided for each vital sign parameter at corresponding visits by treatment and respective changes from baseline. Subjects with vital signs outside of a pre-specified range will also be listed.

The following criteria will be used to determine vital sign results that are outside of a pre-specified range, where changes from baseline are based on matched postural positions and are calculated as parameter value - baseline parameter value:

Table 3: Vital sign parameter cut-off values

Heart Rate(bpm)	Value $>$ 100 and change from baseline $>$ 30, or Value $<$ 55 and change from baseline $<$ -15
Systolic BP(mmHg)	Value $>$ 140 and change from baseline $>$ 20, or Value $<$ 90 and change from baseline $<$ -20
Diastolic BP(mmHg)	Value $>$ 90 and change from baseline $>$ 10, or Value $<$ 55 and change from baseline $<$ -10
Respiration(breaths/min)	Value $>$ 16 or change from baseline $>$ 10

Table 3: Vital sign parameter cut-off values

Heart Rate(bpm)	Value > 100 and change from baseline > 30, or Value < 55 and change from baseline < -15
Temperature (°C)	Value > 38.3°C or change from baseline > 1.6°C

7.6.8.3 Physical Examination Findings

All physical examination abnormal findings will be listed per subject by visit.

7.7 Pharmacokinetic Analysis

Summary statistics of Ctrough (mean, SD, geometric mean, % CV, median, min, and max) for the PK analysis population by treatment and study day.

The listing of Concentration of BMS-986142 by treatment and study day will be provided as well.

[REDACTED]

[REDACTED]

[REDACTED]

[REDACTED]

[REDACTED]

[REDACTED]

7.9 Interim Analyses

After about 20 subjects per treatment arm have completed at least 4 weeks of the treatment period or discontinued the treatment, an interim analysis will be conducted to assess the efficacy of the BMS-986142 dose arms and the overall safety. The interim analysis will use pre-specified efficacy, safety and PK endpoints. The results of the interim analysis will be reviewed by an unblinded sponsor team who is not involved in the study conduct and who will provide recommendations with regard to the adaptive design decisions to the blinded study team.

Population PK and exposure-response analysis may be performed to support the statistical Bayesian analysis and to facilitate decisions around dose selection. Population PK analysis to characterize the PK of BMS-986142 may be performed by pooling data from the present study with the Phase 1 study IMXXXXXX, in order to supplement the PK data as well as test for covariate effects, including but not limited to demographics, disease state, concomitant medications, etc. Exposure-response analysis may be performed using DAS28-CRP as the primary endpoint to characterize the relationship between measures of BMS-986142 exposure and reduction in DAS28-CRP. Details regarding the data evaluation and modeling methodology for interim analysis will be provided in a separate modeling and simulation analysis plan.

Efficacy analysis (DAS28) using Bayesian modeling and dose/exposure response analysis:

The interim analysis will be performed on all available data of DAS28 change from baseline up to Week 12 using a Bayesian predictive approach.¹³ This analysis assumes that the DAS28 at Week 4 and at Week 12 in the subjects who have not yet been observed will be similar to what was observed for the subjects included at Week 4 and Week 12, respectively. As such the unobserved data will be simulated from the predictive distribution conditional on the interim data and the prior distribution of the treatment difference (using a non-informative prior). Under the Bayesian framework, the posterior distribution of the treatment difference (BMS-986142 active dose – Placebo) will be constructed to determine the predictive probability of $\Delta\Delta\text{DAS28}$ improvement greater than a cutoff value at the planned end of the trial for each dose arm.

Note: $\Delta\Delta\text{DAS28}$ improvement: The difference of change from baseline in DAS28-CRP between active dose arm and placebo arm. The lower is the DAS28 score, the better is the disease status.

The Bayesian predictive analysis and the dose/exposure response analysis will determine if new BMS-986142 dose(s) will be needed to fully characterize dose-efficacy relationship. Pre-specified efficacy endpoint (DAS28) will be assessed with exposure endpoints to guide the selection of new dose levels in different scenarios as described below. Considering the safety margin estimated from non-clinical studies, new dose levels based on the interim analysis will not be greater than 350 mg/day.

If the predictive probability of $\Delta\Delta\text{DAS28}$ improvement being greater than 1.0 is high (eg, > 80%) in all active arm(s), the BMS team may recommend to maintain the study design and treatment arms. In this scenario, all enrolled subjects will continue the treatments without modifications and also be included in the final analysis for the existing dose arm. The BMS team may also recommend adding an additional dose arm at lower dose level than current active doses to explore the suboptimal dose. In this case, up to 41 subjects will be randomized into the suboptimal dose arm along with existing efficacious dose arms. The new suboptimal dose level may be selected based on dose/exposure response analysis. In support of adding new dose arm (suboptimal dose or middle dose(s) as described below), population exposure-response analysis may be conducted for the time-course of DAS28-CRP scores and/or selected safety endpoints collected until the interim analysis using a mixed effects inhibitory Emax model, or other alternative models, with respect to time and BMS-986142 exposure.

If the predictive probability of $\Delta\Delta\text{DAS28}$ improvement being greater than 1.0 is high (eg, >80%) in 2 BMS-986142 arms (mid and high dose arms), then the BMS team may recommend to maintain the study design and these 2 treatment arms. The enrolled subjects will be carried over in the existing dose arm and also be included in the final analysis for the existing dose arm. The subjects enrolled in the low dose arm will continue the treatment only if they have received at least 1 treatment and treatment is considered safe before the interim analysis is completed. However, no new subjects will be enrolled in this treatment arm. Based on the dose/exposure response analysis, new dose levels may be added to further characterize the steep portion of the dose-response relationship if the existing 2 consecutive dose levels show a relatively flat exposure response.

If the predictive probability of $\Delta\Delta\text{DAS28}$ improvement being greater than 1.0 is high (eg, $> 80\%$) in 1 BMS-986142 arm (high dose arm), then the BMS team may recommend to maintain the study design and this treatment arm. The enrolled subjects will be carried over in the existing dose arm and also be included in the final analysis for the existing dose arm. The subjects enrolled in the low and mid dose arms will continue the treatment only if they have received at least 1 treatment and treatment is safe before the interim analysis is completed. However, no new subjects will be enrolled in this treatment arm. Based on the dose/exposure response analysis, up to 2 new dose levels may be added to adequately characterize the dose-response relationship.

If the predictive probability of $\Delta\Delta\text{DAS28}$ improvement being greater than 0.6 is low (eg, $< 20\%$), that dose arm is deemed futile in terms of DAS28-CRP change from baseline. However, the final futility will also incorporate the results from other efficacy endpoints as defined below.

The proposed stopping rules at the interim analysis, based on the futility assessment and the overall safety assessment, are as follows:

- Rule 1: If safety issues are identified in all dose arms or all dose arms are futile, stop the study
- Rule 2: Drop the dose arm(s) with safety issues identified
- Rule 3: Drop the futile dose arm(s) and the dose arm cannot be dropped until the lower dose arm has been dropped.

If the predictive probability of $\Delta\Delta\text{DAS28}$ improvement being greater than 0.6 is lower than 20% in all active treatment arms, BMS team may recommend stopping further enrollment and continuing those subjects receiving therapy up to 12 weeks.

Descriptive efficacy analysis (other efficacy endpoints):

In addition to Bayesian predictive analysis above, the following as-observed clinical data up to database lock will be summarized at the time of Week 4 interim analysis to facilitate decision-making.

- ACR20/50/70 response over time
- DAS28-CRP < 2.6 , DAS28-ESR < 2.6 , CDAI ≤ 2.8 , SDAI ≤ 3.3 and Boolean remission over time
- Change from baseline in DAS28-CRP, DAS28-ESR, CDAI, SDAI over time.

Descriptive safety analysis:

For the following pre-specified safety endpoints:

- AE/SAE (including but not limited to hypertension, diarrhea, neutropenia)
- Change from baseline in vitals including systolic blood pressure (SBP) and diastolic blood pressure (DBP).

The study will be stopped if intolerable safety events are identified in all treatment arms. If intolerable safety events are identified in 1 or 2 treatment arms, these arms will be dropped and

the study will be continued with caution. New dose levels may be added based on the exposure response analysis (not greater than 350 mg daily). If intolerable safety events show a clear relationship with higher exposure of BMS-986142, a lower dose will be selected where the predicted exposure in ~ 90% of subjects does not exceed the exposure ranges associated with safety findings.

Based on the totality of safety and efficacy considerations, unsafe dose arm will be stopped immediately. The dose arm(s) that are projected to be ineffective will continue till the end of double-blind period for subjects already taking at least one dose of study medication and no new subjects will be enrolled into ineffective dose arm(s).

[REDACTED]

